### **Project Design and Protocol:**

Open-label randomized controlled study with a 2:1 enrollment ratio of systemic anticoagulation using enoxaparin subcutaneous (or unfractionated heparin in those with a creatinine clearance (CrCl) <30 ml/m^2) in patients with COVID-19 and acute hypoxic respiratory failure.

**Study Procedure:**

1. Patients admitted to HFH with suspected/identified COVID-19 infection will be reviewed daily
2. Those patients that fulfill the inclusion / exclusion criteria will be approached regarding participation in the study. If the patient is intubated, their designated representative will be approached regarding participation in the study.
3. If after answering all questions they agree to participate, an Informed Consent Form will be signed with a copy provided to the patient or their representative.
4. After enrollment, participants will be randomly assigned in a 2:1 ratio to the intervention or standard care control arm. Randomization will be stratified by stable/non-stable status and creatine clearance rate, using sequentially numbered, opaque, sealed envelope (SNOSE) technique for the allocation concealment.
5. Once enrolled, the primary patient history and laboratories will be reviewed, and data collected.
6. Orders for Enoxaparin or high intensity unfractionated heparin IV will be started within six hours of enrollment:
  - a. Options for stable patient (no procedures, hemodynamically stable):
    - i. CrCl  $\geq$  30 mL/min: Enoxaparin 1 mg/kg Q 12 hours
    - ii. CrCl of 15-29 mL/min: Enoxaparin 1 mg/kg Q 24 hours
    - iii. CrCl  $<$  15, rapidly fluctuating renal function, AKI/ESRD on IHD or CRRT: Heparin infusion at 12 units/kg/hr without initial bolus targeting aPTT 1.5-2.5 (55-75 seconds) normal range; dosing and monitoring per the HFH Low Intensity Heparin Protocol Guidelines. (21)
  - b. Options for unstable patient (anticipated procedures, hemodynamically unstable, severe critically illness):
    - i. Heparin infusion at 12 units/kg/hr without initial bolus targeting aPTT 1.5-2.5 (55-75 seconds) normal range
7. Duration of study anticoagulation:
  - a. No acute venous thromboembolism: anticoagulation throughout hospital stay and for six weeks post discharge.
  - b. New acute indication (DVT, PE, atrial fibrillation) for anticoagulation that develops during study treatment: 3 months; agent selection based on treatment team.
8. In the event of development of
  - a. Suspected or confirmed heparin induced thrombocytopenia without thrombosis (isolated HIT): (22-25)
    - i. Treat patient for 4 weeks with one of the following options given the clinical scenario:
      1. Options for stable patient (no procedures, hemodynamically stable):
        - a. CrCl  $\geq$  30 and weight  $>$  50 kg: Fondaparinux 2.5 mg SubQ Daily
        - b. CrCl  $\geq$  30: Rivaroxaban 15 mg PO BID x 15 days, then 20 mg PO QD

- c. CrCl < 30: Apixaban 5 mg PO BID
  2. *Option for unstable patients (anticipated procedures, hemodynamically unstable, severe critically illness):*
    - a. Bivalirudin – goal PTT 1.5-2.5 times baseline PTT; dosing and monitoring per the HFHS HIT Guidelines. (Appendix A)
      - i. CrCl >60 mL/minute: 0.15 mg/kg/hr
      - ii. CrCl 30 to 60 mL/minute: 0.08 mg/kg/hr
      - iii. CrCl <30 mL/minute or dialysis: 0.05 mg/kg/hr
      - iv. CRRT: 0.07 mg/kg/hr
    - b. Suspected or confirmed heparin induced thrombocytopenia with thrombosis (HITT):
      - i. Treat patient for 3 months with one of the following options given the clinical scenario:
        1. *Stable patients (no procedures, hemodynamically stable):*
          - a. CrCl < 30: Apixaban 10 mg PO BID, then Apixaban 5 mg PO BID thereafter
          - b. CrCl ≥ 30: Fondaparinux
            - i. Weight < 50 kg: 5 mg SubQ Daily
            - ii. Weight 50-100 kg: 7.5 mg SubQ Daily
            - iii. Weight > 100 kg: 10 mg SubQ Daily
          - c. CrCl ≥ 30: Rivaroxaban 15 mg PO BID x 15 days, then 20 mg PO QD
        2. *Unstable patients (anticipated procedures, hemodynamically unstable, severe critically illness):*
          - a. Bivalirudin: goal PTT 1.5-2.5 times baseline PTT; dosing and monitoring per the HFHS HIT Guidelines
            - i. CrCl >60 mL/minute: 0.15 mg/kg/hr
            - ii. CrCl 30 to 60 mL/minute: 0.08 mg/kg/hr
            - iii. CrCl <30 mL/minute or dialysis: 0.05 mg/kg/hr
            - iv. CRRT: 0.07 mg/kg/hr
  9. The patients will be monitored after the initiation of therapy.
    - a. The first follow-up will be twelve hours after the start of anticoagulation.
    - b. Evaluation of clinical status will be completed twice daily to monitor progression of hypoxemia, respiratory failure, development of ARDS.
    - c. Daily laboratory testing including CBC with differential, electrolytes, PT, aPTT, INR, D-Dimer.
    - d. Ferritin, LDH, Triglycerides will be checked QOD as per Henry Ford Hospital COVID-19 Management guidelines.
  10. All patients who are in the control group will receive standard of care therapy inclusive of VTE prophylaxis and proning if part of routine care.

11. Post-discharge follow-up:
  - a. Patients will be maintained on anticoagulation upon discharge.
  - b. Patient contact 2 weeks post discharge
  - c. D-Dimer to be drawn at 4 weeks
  - d. Patient contact 6 weeks post discharge
    - i. If D-Dimer remains elevated, discussion regarding continuation of anticoagulation vs. evaluation of VTE.

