In an epidemiologic study in China evaluating the Wuhan population, the investigators found that 17% of patients developed ARDS. (8) Another retrospective evaluation in Wuhan, China of 109 patients who died of complications of SARS-CoV-2 versus 116 patients who survived, reported that 89.9% of those who died had developed ARDS versus 7.6% in the group that survived. (9) In another study, it was identified that the median time from admission to ARDS was two days. (10) Historically in the United states the mortality rates of ARDS are 25% to 40%. (11) The initial reports strongly suggest that the development of ARDS as a result of SARS-CoV-2 may have a higher mortality rate than ARDS due to different etiologies.

There is very little information regarding the histopathological features in COVID-19 infections. In one study two patients who both underwent lung resection for adenocarcinoma were later found to be COVID-19 positive after the operation. (12) Review of the histopathology demonstrated non-specific edema, pneumocyte hyperplasia, focal inflammation, and multinucleated giant cells (no hyaline membranes). In another report of a patient who had died of COVID-19, histopathologic evaluation of the lung tissue demonstrated findings of diffuse alveolar damage with exudates, with predominately lymphocytic inflammation, multinucleated giant cells, and large atypical pneumocytes. (13)

ARDS is an acute diffuse, inflammatory lung injury, leading to increased pulmonary vascular permeability, increased lung weight, and loss of aerated lung tissue with hypoxemia and bilateral radiographic opacities associated with increased venous admixture, increased physiological dead space and decreased lung compliance. (14) The

definition includes an acute onset ( $\leq 1$  week), bilateral opacities consistent with pulmonary edema, a reduced  $\text{PaO}_2/\text{FiO}_2$  (P/F) ratio ( $<100$  severe, 100-200 moderate, 200-300 mild), not explained by fluid overload or congestive heart failure (CHF)

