### **Subjects in the Project:**

#### Inclusion Criteria non vented:

1. Males and Females 18 to 70 years of age
2. Lab confirmed COVID-19
3. Patients with progressive increase in supplemental oxygen requirements, developing acute hypoxic respiratory failure as defined by SaO2 < 93% on ≥6L supplemental oxygen.
4. D-Dimer > 1 µg/ml

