**Justification for Number of Subjects or Data:**

Sample size estimate suggest that 1031 participants are required.

The primary outcome measure for the power calculation is the difference of intubation rate between intervention arm (systemic anticoagulation using enoxaparin subcutaneous (or unfractionated heparin) and control arm (current standard care). We expect the intervention arm will provide a reduction by 30%. The baseline intubation rate was estimated 25 % in the control arm. Assuming alpha at two-sided 0.05 and power at 80% indicates that a total sample size of 1031participants (687 in the intervention and 344 in the control arm) would be required.

Required sample sizes	
Assuming 80% power, alpha=0.05 and two-sided testing	
Reduced by	Estimated intubation rate in COVID-19 inpatients with standard care
10%	10181 (6787:3394)
20%	2435 (1623:812)
30%	1031 (687:344)
40%	548 (365:183)
50%	329 (219:110)

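### Eligibility does not exclude patients whose intubation is already decided or who have a do-not-intubate decision, and power is sensitive to their unknown share

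*Protocol*

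**What the plan says.** **Entry.** Criterion 3, in both the Cheat Sheet and Subjects in the Project, admits "Patients with progressive increase in supplemental oxygen requirements, developing acute hypoxic respiratory failure as defined by" a saturation below 93% on at least 6 L of oxygen. That is a floor with no ceiling. The bar on ventilated patients is criterion 4 of the Cheat Sheet; in Subjects in the Project it survives only as a word in the list's heading. None of the eight exclusions mentions planned intubation or a do-not-intubate decision. Exclusion 8 concerns contraindications in the attending physician's view, which is a different matter.

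**Treatment start.** Study Procedure has patients reviewed daily. Step 6 says orders "will be started within six hours of enrollment". Step 6b is a branch headed "Options for unstable patient (anticipated procedures, hemodynamically unstable, severe critically illness", and stable/non-stable status is a randomisation stratum (Study Procedure step 4; Randomization).

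**Consent.** Study Procedure step 2 provides for approaching a representative when the patient is already intubated.

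**Endpoint and analysis.** The primary endpoint is progression to mechanical ventilation (Outcomes), with no rule for very early events. Data Analysis specifies intention to treat.

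**Sample size.** "The baseline intubation rate was estimated 25 % in the control arm"; "We expect the intervention arm will provide a reduction by 30" per cent; "Sample size estimate suggest that 1031 participants are required".

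**The concern.** The rationale is that anticoagulation interrupts a progressive thrombotic process before respiratory failure. A patient whose intubation is already decided at randomisation carries little information about that. With up to six hours allowed from enrollment to treatment, the event can come before the first dose. A patient with a do-not-intubate decision cannot contribute a primary event in either arm.

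Both groups stay in the analysis, as they must under intention to treat. Events already settled at entry fall on both arms alike and pull the observed effect toward zero. Stratifying by stable/non-stable status balances such patients between arms but does not remove the dilution. In the intervention arm they also take on the bleeding risk of assigned anticoagulation when the primary endpoint may no longer be open to change. This cannot be repaired after enrollment, because dropping early events later would break the intention-to-treat rule.

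**Working it through.** **Inputs from Justification for Number of Subjects or Data:** control rate 25%, relative reduction 30% (so 17.5%), two-sided alpha 0.05, power 80%, arms 687:344. **Assumed, not in the protocol:** the share f of control-arm intubations already settled at entry, taken as 5% to 30%, and a 5% do-not-intubate share.

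**1. Reproduce the plan's figure.** Two proportions, pooled variance under the null, 2:1 allocation:

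n_c = [1.960·√(1.5·p̄(1−p̄)) + 0.842·√(p_c(1−p_c) + p_t(1−p_t)/2)]² / (p_c−p_t)²

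With p̄ = (0.25 + 2×0.175)/3 = 0.20, the bracket is 0.960 + 0.429 = 1.389, and 1.389²/0.075² = 343.02. Rounding each arm up gives 344 and 2×343.02 → 687, total 1031, as stated. Power at 687:344 is Φ[(0.075 − 1.960×0.02642)/0.02748] = Φ(0.845) = 80.1%. The plan's arithmetic is right.

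**2. Model A: settled cases lie within the 25%.** The 30% reduction applies only to the other events, so p_t = 0.25f + 0.25(1−f)(0.7).

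**3. Model B: the same number of patients comes on top.** Their share of all patients is s = 0.25f. All of them are intubated, and the rest have 25% versus 17.5%. Then p_c = s + 0.25(1−s) and p_t = s + 0.175(1−s).

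| f | A: p_t | A: overall reduction | A: power | s | B: p_c vs p_t | B: power |
|---|---|---|---|---|---|---|
| 5% | 17.88% | 28.5% | 75.7% | 1.25% | 25.94% vs 18.53% | 77.8% |
| 10% | 18.25% | 27% | 70.9% | 2.5% | 26.88% vs 19.56% | 75.5% |
| 20% | 19.00% | 24% | 60.3% | 5% | 28.75% vs 21.63% | 70.9% |
| 30% | 19.75% | 21% | 49.0% | 7.5% | 30.63% vs 23.69% | 66.4% |

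For scale, 344 × 0.25 = 86 control intubations are expected, so f = 10% is about nine of them. To keep an overall 30% reduction under model A, the effect on the remaining events would have to be 0.30/(1−f): 31.6%, 33.3%, 37.5% or 42.9%.

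**4. Do-not-intubate patients.** If 5% of patients cannot have the event and f = 20%, the rates are 0.95×25% = 23.75% and 0.95×19% = 18.05%. Power is 57.7% instead of 60.3%.

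**5. What exclusion recovers under model A.** Removing settled cases also lowers the control rate, to 0.25(1−f)/(1−0.25f), with the full 30% reduction among those left.

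| f | Control rate after exclusion | Power, not replaced | Power, replaced to 1031 | Power without exclusion |
|---|---|---|---|---|
| 5% | 24.1% | 77.7% | 78.2% | 75.7% |
| 10% | 23.1% | 75.1% | 76.2% | 70.9% |
| 20% | 21.1% | 69.4% | 71.6% | 60.3% |
| 30% | 18.9% | 63.0% | 66.2% | 49.0% |

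Exclusion helps in every row, but 80% is not restored at 1031.

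**The case against.** The strongest reply is that the power loss follows from reinterpreting the assumption. The plan states the 30% as an effect of the whole intervention arm against an arm-wide rate, so it may already allow for patients who cannot benefit. That stands: the loss is conditional on reading the 30% as the effect on preventable events. Nothing in the sample-size section says that an allowance was made, so the question stays open.

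Model A is also the harsher model. The sample-size table describes its rate as that of COVID-19 inpatients on standard care, not of patients failing on 6 L or more, so a higher trial rate is plausible. That also stands, and is why model B is shown.

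The inclusion of unstable patients looks deliberate, and they still inform mortality, ventilator and ICU days, and thrombosis. Agreed; the point concerns only the two narrower groups.

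A reader might go further and infer three things that the protocol does not support:
- That patients awaiting intubation **are** being randomised. The text permits this by silence; it does not say so. Step 6b selects a treatment and is not an entry rule, and its procedures are not defined as intubation.
- That treatment **cannot** act in time. No onset time is given, and six hours is a maximum. The Background's statement that "the median time from admission to ARDS was two days" runs from admission to ARDS, not from enrollment to intubation, and is eight times the start window (48/6).
- That 30% and 80% are **not deliverable**. The figures reproduce, and the share that would undermine them is unknown.

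**Conclusion.** The gap is real and worth closing; its size is unknown. Eligibility fixes how sick a patient must be but does not keep out those whose intubation is already decided or ruled out. Under the protocol's own timetable, a primary event can precede any study drug.

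Over assumed shares of 5% to 30% of control intubations, power falls from 80.1% to between 75.7% and 49.0% if these cases lie within the 25%, or to between 77.8% and 66.4% if they come on top of it. Do-not-intubate patients add a smaller loss, 2.6 points in the case computed. All of this rests on the assumed shares and on the 30% applying only to events still open to change. The supportable statement is that the planned power is sensitive to a group that eligibility does not address, not that the design fails.

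One related defect needs no assumption: Study Procedure step 2 provides for consent on behalf of an intubated patient, while Cheat Sheet criterion 4 bars ventilated patients. An already ventilated patient cannot progress to the primary endpoint.

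**What to change.** 1. Add two lines to both exclusion lists (Cheat Sheet and Subjects in the Project), checked immediately before the envelope is opened: (a) a decision to intubate has already been made at the time of randomisation; (b) a do-not-intubate decision is in place.
2. Record the times of randomisation, first dose and intubation. Report by arm, descriptively, the primary events before first dose. The control arm has no first dose, so also count events in both arms within six hours of enrollment, the protocol's own start limit. These events stay in the intention-to-treat analysis.
3. Reconcile Study Procedure step 2 with Cheat Sheet criterion 4, and give the numbered list in Subjects in the Project the same wording on ventilation.
4. State in the sample-size section whether the 30% is meant to cover all randomised patients, including those intubated very early.

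**Cost:** two eligibility lines, three time stamps and some wording. Recruitment is slightly slower, and the control event rate somewhat lower. For an assumed 10% share, power goes from 70.9% to about 75% without replacement or 76% with it; for 20%, from 60.3% to about 69% or 72%. The change recovers part of the loss. Reaching 80% in those cases would need more patients.

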**Outcomes:**

1. Primary Endpoint:
  - a. Progression to require mechanical ventilation
2. Secondary Endpoints:
  - a. Day 28 all-cause mortality
  - b. Ventilator days
  - c. ICU days
  - d. Central catheter thrombotic events
  - e. Diagnosed VTE
3. Exploratory Endpoints:
  - a. Change in D-Dimer
  - b. Change in Ferritin
  - c. Change in CRP
  - d. Change in LDH
  - e. Change in Triglycerides

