### **Adverse Events:**

Patients will be followed for 28 days during which time. All adverse events (AE) and serious adverse events (SAE) will be recorded including, but not limited to:

1. Minor Bleeding: Any sign or symptom of hemorrhage (i.e., more bleeding than would be expected for a clinical circumstance, including bleeding found by imaging alone) that does not fit the criteria for the definition of major bleeding but does meet at least one of the following criteria:
  - i. requiring medical intervention by a healthcare professional
  - ii. leading to hospitalization or increased level of care
  - iii. prompting a face to face (i.e., not just a telephone or electronic communication) evaluation (26)
2. Major bleeding: Bleeding in non-surgical patients is defined as having a symptomatic presentation and 1:
  - i. Fatal bleeding, and/or
  - ii. Bleeding in a critical area or organ, such as intracranial, intraspinal, intraocular, retroperitoneal, intra-articular or pericardial, or intramuscular with compartment syndrome, and/or
  - iii. Bleeding causing a fall in hemoglobin level of  $20 \text{ g L}^{-1}$  ( $1.24 \text{ mmol L}^{-1}$ ) or more, or leading to transfusion of two or more units of whole blood or red cells. (26)
3. Thrombocytopenia (Heparin induced)

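### Post-discharge contacts and D-dimer are not extended to controls, so diagnosed VTE, which has no time window, can be looked for more closely in treated patients (minor)

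*Protocol*

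**What the plan says.** The trial is described as an "Open-label randomized controlled study with a 2:1 enrollment ratio". Four parts of the Protocol bear on how VTE is found after discharge.

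- **Study Procedure, item 7** ("Duration of study anticoagulation"): without a VTE, study anticoagulation runs through the hospital stay and six weeks beyond discharge.
- **Study Procedure, item 10**: controls receive standard care, including VTE prophylaxis, and proning where routine. Nothing after discharge is mentioned.
- **Study Procedure, item 11**: 11a, "Patients will be maintained on anticoagulation upon discharge"; 11b, "Patient contact 2 weeks post discharge"; 11c, "D-Dimer to be drawn at 4 weeks"; 11d, a second contact at six weeks, with sub-item 11d.i, "If D-Dimer remains elevated, discussion regarding continuation of anticoagulation vs. evaluation of VTE". No arm is named anywhere in item 11.
- **Outcomes and Adverse Events**: "Diagnosed VTE" is a secondary endpoint with no time window, whereas mortality is fixed at day 28. Under Adverse Events, patients are followed for 28 days and "All adverse events (AE) and serious adverse events (SAE) will be recorded including, but not limited to" the listed bleeding and thrombocytopenia events. That section is not limited to one arm.

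**The concern.** A diagnosed VTE depends on someone asking or testing. If staff apply item 11 to treated patients only, those patients have two scheduled contacts and a blood test after discharge. Controls have only general adverse-event recording, for which no contact or test is specified. Everyone knows the allocation, so blinding does not even out the effort. Because the endpoint has no window, nothing in the Protocol excludes events found through the extra follow-up.

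Under this reading the bias would run against anticoagulation, since more of its post-discharge events would be found. A comparison of VTE is of obvious interest in an anticoagulation trial. Contacts that were never made in one arm cannot be recovered at analysis, whatever a statistical analysis plan says.

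**Working it through.** **1. Whom does item 11 cover?**

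| Item | Arm named? | What the content implies |
|---|---|---|
| 11a anticoagulation after discharge | No | Intervention arm: item 7 defines this as study treatment |
| 11b contact, 2 weeks | No | Open |
| 11c D-dimer, 4 weeks | No | Open |
| 11d contact, 6 weeks | No | Open, but coincides with the end of study anticoagulation (item 7a) |
| 11d.i D-dimer rule | No | A patient already anticoagulated, since it speaks of continuing |
| Item 10 (controls) | Yes | No post-discharge procedure |

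Applying all of item 11 to both arms would anticoagulate controls after discharge, which does not fit item 10. Applying it to the intervention arm only leaves controls with no scheduled contact. The text does not choose a third reading, 11a for treated patients and the rest for both.

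**2. What falls within 28 days?** Let *d* be the day of discharge counted from randomisation, and take item 11 as timed from discharge (an inference from its heading for 11c, which gives no origin).

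- 2-week contact: day *d* + 14, which is by day 28 only if *d* ≤ 14.
- 4-week D-dimer: day *d* + 28, after day 28 for any *d* > 0.
- 6-week contact: day *d* + 42, after day 28.

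With a day-28 window, the D-dimer therefore hardly bears on the endpoint. The contacts still do, because even a late contact can bring to light a VTE diagnosed elsewhere before day 28.

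**3. The Protocol's own figure.** Control rate 25%, 30% reduction to 17.5%, 2:1, two-sided 0.05, 80% power. The pooled rate is (0.25 + 2 × 0.175)/3 = 0.20.

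n(control) = [1.960 × √(0.20 × 0.80 × 1.5) + 0.842 × √(0.25 × 0.75 + 0.175 × 0.825/2)]² / 0.075² = 343.0, rounded up to 344.

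The intervention arm is 2 × 343.0 = 686.05, rounded up to 687, and the total is 1031, as stated. Power at 687:344 is 80.1%. No VTE assumption enters.

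**4. Illustration of size.** The Protocol gives no VTE rate, so every input here except 687:344 is an assumption. Let *r* be the true VTE risk in both arms (no treatment effect), *s* the share of events occurring after discharge and within the window, and *q* the fraction of those captured in controls. Capture in treated patients is complete.

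- Observed control risk = *r*(1 − *s*(1 − *q*))
- Missed control events = 344 × *r* × *s* × (1 − *q*)
- False harm = chance that a two-sided 5% test of two proportions (normal approximation) favours control; 2.5% if ascertainment is equal

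| *q* | *s* | *r* | Missed control events | Observed risk ratio | False harm |
|---|---|---|---|---|---|
| 0.9 | 20% | 3% | 0.2 | 1.02 | 2.8% |
| 0.9 | 40% | 10% | 1.4 | 1.04 | 3.9% |
| 0.5 | 5% | 3% | 0.3 | 1.03 | 2.9% |
| 0.5 | 10% | 10% | 1.7 | 1.05 | 4.3% |

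The last row in full: 344 × 0.10 × 0.10 × 0.5 = 1.7 events; observed control risk 0.10 × (1 − 0.10 × 0.5) = 9.5%; ratio 10/9.5 = 1.05.

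The first pair describes adverse-event follow-up that works well; the second describes few events between discharge and day 28, half of them missed in controls. Without a window, *s* has no limit set by the document, so no upper bound can be given.

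**The case against.** The strongest defence is that the Adverse Events section already follows every patient for 28 days and records all adverse events. A diagnosed VTE is an adverse event in either arm, and 28 days is also the mortality window. The counting window may be set in a statistical analysis plan that is not shown. Within 28 days, the only scheduled item that differs is one contact, in patients discharged by day 14. This largely stands, and it is why the point is minor. It does not remove the point: that section schedules no contact, and an analysis plan can set a window but cannot supply contacts that controls never had.

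A reader might infer more in three ways.

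- *Controls certainly go unfollowed after discharge.* The text does not say so. Item 11 speaks of patients generally, and the sponsor may intend the contacts for both arms.
- *Item 11d.i lets treated patients continue anticoagulation in place of a VTE work-up, which would favour treatment.* It calls for a clinical discussion, does not bar evaluation in those who continue, and falls after day 28. It is not a rule for ascertaining the endpoint.
- *The false-positive rate for VTE is seriously inflated.* Large figures require assumed event rates and capture fractions for which the document gives no basis.

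**Conclusion.** The point holds as a minor one. Item 11 is built around anticoagulated patients and does not extend post-discharge contacts or the D-dimer to controls. Diagnosed VTE has no window, and allocation is known. Unequal ascertainment after discharge is therefore possible, with the 28-day adverse-event follow-up as the only safeguard common to both arms.

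The document does not determine the size. In the illustrated 28-day settings, fewer than two control events are missed and false harm is 2.9% to 4.3% if half of few post-discharge events are captured, or 2.8% to 3.9% if 90% of a larger share are, against 2.5%. These figures rest on an assumed VTE risk of 3% to 10%, no true effect and complete capture in treated patients. If the sponsor already makes the contacts in both arms, only the wording and the window need attention. The primary endpoint (mechanical ventilation), day-28 mortality and the sample size of 1031 are not affected.

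**What to change.** In Study Procedure, item 11:

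- 11a: *Intervention arm only.*
- 11b and 11d, contacts: *Both arms, on the same schedule and with the same questions about VTE.*

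In Outcomes: *Diagnosed VTE is counted from randomisation to day 28 in both arms*, matching mortality and adverse-event follow-up.

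With that window, 11c and 11d.i can remain as clinical guidance for treated patients and need not feed the endpoint. If the sponsor wants VTE after day 28 to count, the 4-week D-dimer must be drawn in both arms as well, which adds up to 344 control tests. A compulsory VTE work-up triggered by D-dimer is not needed; it would add imaging, and under a day-28 window it would contribute nothing to the endpoint.

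The cost is three lines of text and, if the contacts were not already meant for controls, up to 2 × 344 = 688 brief control contacts.
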